4.9 Endpoints

Primary endpoint:

- Sensitivity in diagnosing SDB of the AL device using AASM 2012 guidelines.

Secondary endpoints:

- The number of predominant obstructive and predominant central events using the AL effort band and flow sensor vs. PSG per AASM 2012 and 2007 Guidelines
- Monitoring times from AL vs total sleep time from PSG per AASM 2012 and 2007 Guidelines
- Number of hypopneas using the AASM 2012 arousal criterion (using monitoring time)
- Positive likelihood ratio in diagnosing SDB using AASM 2012 and 2007 guidelines

4.10 Investigational Devices

ApneaLink Air

The ApneaLink Air is a market-released device that has been FDA-cleared (K143272) for use by Health Care Professionals for screening and diagnosis of SDB for adult patients. The device records the following data: patient respiratory nasal airflow, snoring, blood oxygen saturation, pulse, respiratory effort and actigraphy. The AL uses these recordings to produce a report that may aid in the diagnosis of sleep disordered breathing or for further clinical investigation.

The AL recorder is a 4-channel battery-powered HSAT device. Patients may perform the recording independently at home. The AL recorder and the respiratory effort sensor must be fastened with the re-usable belt on the patient's chest. All relevant respiratory information during sleep will be collected via nasal cannula, pulse oximetry adapter, actigraphy sensor and respiratory effort sensor. The disposable plastic nasal cannula is connected to the AL recorder and fixed at the patient's nose. The oximetry sensor is connected to the patient's finger. The respiratory effort sensor is connected to the AL recorder and held in place by the belt. The physician can generate a report containing automated sleep data from the device.

See ApneaLink Air Clinician's Manual for more details.

Labeling

Devices will be labeled to contain the information as required by relevant regulatory requirements:

- a) Sponsor name and address
- b) Serial number to identify the individual device
- c) Instruction for Use (Appendix)

4.11 Data Collection Method and Storage

4.11.1 Data Collection

All data from the study will be documented via:

- CRFs (Appendix)
- Sleep study reports (AL and PSG reports and EDF files)

Participant identification will be coded to maintain confidentiality

ApneaLink Air

The ApneaLink Air will be set up by sleep lab staff. Participants and site staff will have access to the AL clinical guide and AL user guide to help with set up.

After testing is complete, reports will be generated with automatic scoring using both AASM 2007 and AASM 2012 Scoring rules. The raw data will be exported and saved in mmrx format. These three reports will be uploaded to the electronic data capture (EDC) system.

PSG

The PSG will be conducted on the participant following the normal procedures of the Sleep Lab. After testing is complete, the unscored EDF and associated technotes file for the PSG will be uploaded to the EDC system. PSGs will be centrally scored by the University of Florida Sleep Lab.

The recording montage should include EEG channels F4-M1, C4-M1, O2-M1, E1-M2, E2-M2, chin EMG (3 electrodes), ECG, nasal pressure, oronasal thermal airflow, snore, thoracic and abdominal effort (uncalibrated RIP), pulse rate, and pulse oximetry. It is preferred to also include channels F3-M2, C3-M2, and O1-M2 as backup electrodes. Body position must be included in the tech notes, or body position sensor included, with video to confirm.

4.11.2 Study Documentation

Throughout the conduct of the study, all required data will be entered into the eCRF for each participant. The investigator should ensure the accuracy, completeness, and timeliness of the data reported to the Sponsor in the eCRFs and in all required reports and will be asked to sign and date the appropriate eCRF page(s) to verify the data collected. Data entered into the eCRF must be consistent with source documents. Any change or correction to an eCRF will be captured in the EDC system audit trail.

The clinical site will provide study data to the Sponsor by recording data in the EDC System (21 CFR Part 11 compliant).

In cases of participant-reported data, the eCRF will be the source record.

The site PI or designee and the clinical monitor will review completed eCRFs for accuracy, discrepancies, and missing information. The information entered into the eCRF will be accessible to the appropriate ResMed Medical Affairs personnel.

4.11.3 Query Generation

Any data queries will be sent to site for reconciliation via the eCRF system and final close-out will be from the study monitor.

4.11.4 Data Storage

All electronic systems used by the site and Sponsor will have adequate security to protect participant privacy and data integrity. All paper documentation will be locked in a secured cupboard. All trial data and documentation will be retained for a minimum of 15 years before it is destroyed. Access to data maintained in the EDC System is strictly limited to authorized personnel.

4.11.5 Inspection of Records

Periodically the Sponsor or representative will review the Investigator study file and the study data to verify compliance with applicable regulations and the protocol, and to verify accuracy of the data.

4.11.6 Study Files and Record Retention

The investigator must maintain adequate and accurate records as specified in Essential Documents for the Conduct of a Clinical Trial (E6, Section 8 of the ICH Guideline for GCP) to enable the conduct of the study to be fully documented and the study data to subsequently be verified. These documents should be classified into two separate categories: (1) investigator's study file and (2) participant clinical source documents.

Essential documents must be retained until at least 2 years after notification by the Sponsor that the investigations have been discontinued OR 2 years after the last approval of a marketing application. The investigator must notify the Sponsor prior to destroying any clinical study records.

4.11.7 Regulatory Documentation

Documents that must be provided to the Sponsor prior to study initiation are:

- Signed, dated current (within 2 years) curriculum vitae of Investigator and Sub-Investigator(s)
- Financial disclosure for physicians and nurses
- Signed (original), dated Investigator Agreement
- Assurance that the IRB complies with requirements set forth in Title 21 Part 56 of the Code of Federal Regulations. The required documentation consists of name and address of the IRB, a current list of members including title, gender, occupation and any institutional affiliation of each member. A general assurance number from the Department of Health and Human Services may be substituted for this list.
- Written notification (copy) to the Investigator from the IRB approving the protocol
- IRB approved informed consent (copy) and any other adjunctive materials to be used in the study as required.

4.11.8 Distribution of Results

Data analyses will be completed by an independent statistician and the clinical study report will be completed by the Sponsor.

4.12 Clinical Study Procedures

Visit 1 – Screening and PSG/HSAT

1. Eligible participants will be identified at the research site via referral, electronic medical record search, database searches or other methods determined by the research site.
2. Participants will be provided verbal and written information on the study, have the opportunity to ask any questions and will provide written informed consent if they elect to participate.
3. The inclusion/exclusion criteria checklist is to be completed by the researcher to assess whether the participant is eligible to participate in the study.
4. If eligible, the participant will be enrolled in the trial through the EDC, which will assign a coded identifier for the participant.
5. Demographics form will be completed in the EDC
6. Participants will be fitted with the AL and PSG equipment
7. Participants will undergo an overnight PSG. Full PSG set-up, data acquisition, monitoring and reporting will be performed using both the AASM 2007 and 2012 criteria. At least 4 hours of recording will be required. Participants with <4 hours of recording time will be asked to repeat the exam.
8. Upload de-identified (subject ID only) PSG files to the EDC system:
 - a. Technotes file
 - b. Scored PSG (optional)
 - c. Unscored PSG
9. Upload de-identified AL files to the EDC system:
 - a. Raw AL data as an mmrx file
 - b. Auto-scored report using AASM 2007 rules
 - c. Auto-scored report using AASM 2012 rules
10. Participant will be provided with a gift card for their participation.

4.13 Informed Consent

The consent form is written in accordance with applicable data privacy acts and FDA regulations and approved by the responsible Institutional Review board (IRB).

The investigator or responsible staff will explain the nature, purpose and risks associated with the study. This will include information regarding testing for sleep disordered breathing. The possible side effects will be explained to the patient. The patient will be given sufficient time to consider the study's implications before deciding whether to participate. Information materials created by the investigators and Sponsor must be approved by the responsible IRB prior to use.

A signed, IRB-approved consent form must be obtained from the patient prior to the performance of any protocol-related testing or treatment procedures. The consent process must be performed by a

designated clinical study team member authorized by the IRB to consent patients and listed on the Delegation of Authority Log as having privileges to consent patients. A signed copy of the consent form must be maintained in the study files and a copy provided to the patient. The patient's medical records should indicate study participation.

4.13.1 Participant Remuneration

Participants will be compensated \$150 for their time and reimbursed at the standard rate for travel required to attend study-required visits and procedures.

Any published and presented data will not include individually identifiable participant information.

5 STATISTICAL ANALYSIS METHODS

Analysis Populations:

All subjects who meet the inclusion and exclusion criteria and who complete at least 4 evaluable hours will be included in the Intention-to-Treat population (ITT). All primary and secondary analyses will be generated for the ITT population.

Primary Analysis:

The diagnostic sensitivity of AL will be estimated as the number of participants with REI \geq 5 events per hour according to AL per AASM 2012 Guidelines divided by the number of participants with AHI \geq 5 events per hour according to PSG. The diagnostic sensitivity of AL will be compared to the threshold of 0.825 (AASM criteria for out-of-center testing devices) with an exact binomial test, using a significance level of 0.025. Further a one-sided 97.5% confidence interval for the diagnostic sensitivity will be calculated using the Wilson score method.

Secondary Analyses:

To compare the numbers of predominant obstructive and predominant central events measured by AL and PSG, each patient will be classified as having (1) fewer than 5 events per hour, (2) 5 to 10 events per hour, (3) 10 to 30 events per hour or (4) more than 30 events per hour. The categories obtained by AL and PSG will be compared with the weighted kappa statistic. Events will be assessed per both the AASM 2012 and 2007 guidelines.

To compare the AL monitoring times to the PSG total sleep times, Bland-Altman plots will be constructed and the 95% limits of agreement will be calculated. Times will be assessed per both the AASM 2012 and 2007 guidelines.

To compare the number of hypopneas measured by AL and PSG, the number of hypopneas per hour will be categorized as follows: (1) fewer than 5 events per hour, (2) 5 to 10 events per hour, (3) 10 to 30 events per hour or (4) more than 30 events per hour. The categories obtained by AL and PSG will be compared with the weighted kappa statistic. Events will be assessed per both the AASM 2012 and 2007 guidelines.

The positive likelihood ratio (the estimated sensitivity divided by 1 minus the estimated specificity) will also be calculated along with the associated one-sided 97.5% confidence interval. The positive likelihood ratio will be compared with the threshold of 5 (AASM criteria for out-of-center testing devices¹²) using a Wald test. The positive likelihood ratio will be calculated per the AASM 2012 and 2007 guidelines.

AEs

A listing of all adverse events reported for each participant enrolled in the study will be presented, including event description, time of occurrence, severity, outcome, action taken and relationship to the study.

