4.2 Study Design

This is a prospective, non-blinded, open label, single arm study to evaluate the AL ability to correctly score SDB compared to the gold standard diagnostic tool, in-lab PSG. All participants will meet the inclusion and exclusion criteria and will sign the informed consent form before any study related procedures are performed. All participants will wear the AL device and undergo concurrent PSG testing. The AL and PSG tests will only be considered evaluable if the evaluation time is ≥ 4 hours. Participants with <4 hours evaluable time will be asked if they would like to repeat the test.

The AL device will be scored automatically using both AASM 2012 and 2007 guidelines. The AL automatic results will be compared with the PSG using all variables identified by the study objectives. These variables are defined in Section 4.7. Results collected in this study may be used for further algorithm and product development that are outside the scope of this protocol.

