4.8 Sample Size Justification

The sample size for this clinical study will be up to 75 eligible participants undergoing PSG.

Recruitment goals are as follows:

- At least 30 men and at least 30 women
- At least 5 participants in each of the following SDB categories (per PSG):
 - No SDB (AHI <5)
 - Mild SDB (AHI 5-14)
 - Moderate SDB (AHI 15-29)
 - Severe SDB (AHI ≥ 30)
- At least 5 participants with CSA
- At least 5 participants in each of the following BMI categories (applies to both men and women):
 - Normal BMI: < 25.0
 - Overweight BMI: 25.0 – 29.9
 - Obese: ≥ 30
- At least 5 participants in each of the following race categories:
 - White
 - Black
 - Asian

The primary objective of this study is to demonstrate the sensitivity in diagnosing SDB per the AASM 2012 guidelines. Sensitivity will be assessed according to the AASM criteria for out-of-center testing devices. The hypotheses tested are:

$$H_0: \pi \leq 0.825 \text{ versus } H_A: \pi > 0.825$$

where π is the sensitivity of AL in diagnosing SDB (using a cut-off of 5 events per hour as the threshold for SDB and AHI from PSG and REI from HSAT). The hypothesis will be tested with an exact binomial test using a one-sided significance level of 0.025.

The required sample size to achieve 80% power was estimated using PASS 14, Tests for One Proportion Procedure, assuming a true sensitivity of 0.95 (13 out of 13 true positives were correctly classified in a previous study). To achieve an 80% probability of rejecting the null hypothesis, a minimum of 56 SDB participants are required. Seventy-five participants will be enrolled in order to meet recruitment goals.

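### The only efficacy set is labelled Intention-to-Treat but is an evaluable-pairs set, so the primary sensitivity is conditional on an evaluable ApneaLink Air (AL) recording, and Section 5 plans no table of AL failures

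*Combined protocol and SAP*

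**What the plan says.** Section 5 (Analysis Populations) defines one efficacy set: participants who meet the eligibility criteria and "who complete at least 4 evaluable hours will be included in the Intention-to-Treat population (ITT"). It adds: "All primary and secondary analyses will be generated for the ITT population". No other efficacy set is defined.

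The primary sensitivity is the number of participants positive on AL "divided by the number of participants with AHI" of at least 5 events per hour on PSG. Section 5 does not say which device the 4 hours refer to.

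Section 4.2 supplies the missing link: "The AL and PSG tests will only be considered evaluable if the evaluation time is" at least 4 hours. It then offers a repeat: "Participants with <4 hours evaluable time will be asked if they would like to repeat the test".

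Step 7 of Section 4.12, the overnight PSG step, uses a different quantity: "At least 4 hours of recording will be required", and "Participants with <4 hours of recording time will be asked to repeat the exam".

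Section 4.7 defines total sleep time and monitoring time, but not evaluable time. Section 9 has technical observations and protocol deviations assessed as sites report them, for their effect on safety or data integrity. Section 5 plans the sensitivity test, weighted kappa, Bland-Altman limits, the positive likelihood ratio and an adverse event listing. It plans no count of non-evaluable tests, repeats or exclusions.

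**The concern.** An intention-to-treat set does not depend on what happens after enrolment. This one does: a participant enters it only if the night yields enough evaluable data. The restriction is stated openly, so nothing is hidden in the definition. The label, however, claims a property that the set lacks.

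The case that matters is a participant with an evaluable PSG, an AHI of at least 5, and an AL recording that is not evaluable after any repeat. Under Sections 4.2 and 5 together, this person leaves the sensitivity denominator. The device under test failed to identify a diseased participant, and the primary result does not register it. Someone who goes home early is different: both recordings are short, and that person belongs in neither denominator.

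At stake is what the reported figure means. A reader told of an ITT sensitivity would take it to include device failures. It would not, and no planned table would show how many there were.

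**Working it through.** **Inputs.** From Sections 4.8 and 5: null sensitivity 0.825; exact binomial test, one-sided alpha 0.025; assumed true sensitivity 0.95; 80% power; "a minimum of 56 SDB participants are required". The AL failure rate is not in the documents, so it is taken as an assumed range of 0% to 10%.

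**Step 1: reproduce the plan's figure.** For each n from 40 upwards, let r be the smallest count with P(X ≥ r | n, 0.825) ≤ 0.025. Power is P(X ≥ r | n, 0.95).
- n = 48: r = 45, power 0.782.
- n = 55: r = 52, power 0.705.
- n = 56: r = 52, exact alpha 0.0229, power 0.853.

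The smallest n from 40 upwards with power of at least 0.80 is 56. The stated figure is reproduced.

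**Step 2: direction.** Let x be the PSG-positive participants detected by AL, n the PSG-positive participants with an evaluable AL recording, and k those with an evaluable PSG but no evaluable AL recording. The conditional sensitivity is x/n. With failures counted as not detected it is x/(n + k). Since k ≥ 0, x/n ≥ x/(n + k), with equality at k = 0 (or x = 0).

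**Step 3: assumed failure rate f.** Counting every failure as not detected, sensitivity = 0.95 × (1 − f). This is a worst case, not an estimate of bias.

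| f (assumed) | Sensitivity with failures counted | P(at least 52 of 56) |
|---|---|---|
| 0% | 0.950 | 0.853 |
| 1% | 0.9405 | 0.761 |
| 2% | 0.931 | 0.656 |
| 5% | 0.9025 | 0.352 |
| 10% | 0.855 | 0.077 |

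**Step 4: results near the boundary.** Here p = P(X ≥ x | n, 0.825), and the lower bound is the one-sided 97.5% Wilson bound named in Section 5.

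| Result | Added AL failures | p | Wilson lower bound |
|---|---|---|---|
| 52/56 | 0 | 0.0229 | 0.830 |
| 52/57 | 1 | 0.0512 | 0.811 |
| 53/56 | 0 | 0.0073 | 0.854 |
| 53/57 | 1 | 0.0201 | 0.833 |
| 53/58 | 2 | 0.0458 | 0.814 |
| 54/56 | 0 | 0.0017 | 0.879 |
| 54/58 | 2 | 0.0177 | 0.836 |

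The critical result, 52/56, does not survive one added failure. 53/56 survives one but not two, and 54/56 survives two. Only results near the boundary are sensitive to a small number of failures.

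**The case against.** The strongest reply is that the name changes no calculation. This is a one-night, single-group diagnostic comparison with no treatment assignment, and Section 5 defines the set in the sentence that names it. The aim is accuracy against concurrent PSG, and no objective or endpoint concerns recording failure, so evaluable pairs suit the purpose. This stands as a reason to keep the primary test where it is. It does not rescue the label, and it does not explain why failures of the device under test go untabulated.

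The second reply is that failures may hardly occur. Section 4.11.1 has lab staff set up the device, and repeats are offered. This also stands. At an assumed 1% rate, the chance of no failure among 57 PSG-positive participants is 0.99^57 = 0.56. Nothing in the documents says that one, two or three failures will occur, so the boundary results are illustrations only.

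Two stronger readings are tempting and are not supported:
- A reader might infer that failures could never be counted. Sections 4.11.1 and 4.12 have the raw AL data, both auto-scored AL reports and the unscored PSG uploaded for each participant, so a count is possible. What is missing is a planned table.
- A reader might infer that two analysts would form different denominators, because Section 4.12 speaks of recording time within the PSG step. That step is a site procedure and does not define an analysis set. Sections 4.2 and 5 share the word evaluable and give one natural reading: both tests. The mismatch in terms is real but minor.

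**Conclusion.** The concern holds as a matter of labelling and reporting. The set called ITT is an evaluable-pairs set. The primary figure is sensitivity conditional on an evaluable AL recording, and it can only equal or exceed the figure with AL failures counted. This rests on reading Section 5 with Section 4.2; Section 5 alone names no device.

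The size is unknown because no AL failure rate is given. Under an assumed 0% to 10%, a sensitivity of 0.95 would fall to between 0.95 and about 0.86 in the worst case. At the critical value, one failure would move p from 0.023 to 0.051.

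A reader might go further and infer that the primary result is biased, that its conclusion is likely to reverse, or that the sample size is wrong. The documents support none of these. The conditional quantity is legitimate, no failure rate is documented, and the stated 56 is reproduced. The change is worth making because it is cheap and tells readers what the figure covers.

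**What to change.** 1. In Section 5, rename the set the Evaluable population, state that the 4-hour condition applies to both AL and PSG, and keep the primary test on it.
2. Add one pre-specified supportive estimate with its interval, in all eligible participants with an evaluable PSG. Count PSG-positive participants without an evaluable AL recording after any permitted repeat as not detected.
3. Tabulate non-evaluable tests by device (AL, PSG, both), reason and PSG status.
4. As a minor clarification, reconcile evaluable time (Sections 4.2 and 5) with recording time (Section 4.12), and state which night is analysed after a repeat.

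The cost is SAP wording, one extra table and a short protocol clarification; no new data or participants are needed. The downside is that the supportive figure can only be equal or less favourable. It should be presented as an estimate, not a test. With 56 SDB participants, the chance of reaching 52 falls from 85% with no failures to 35% at an assumed 5%, so it would be underpowered as a test.

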3 OBJECTIVES

The aim of this study is to evaluate the accuracy of the ResMed ApneaLink Air device (AL) as it compares to PSG. The AASM criteria for out-of-center testing devices are used to evaluate the accuracy of AL¹². Specifically, the sensitivity in diagnosing SDB of the ResMed ApneaLink Air device will be estimated per AASM 2012 guidelines and compared to the threshold of 0.825. Participants will use an AL device while undergoing concurrent PSG, which will be considered the gold standard for the estimate of sensitivity.

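### The primary sensitivity formula in Section 5 counts every ApneaLink-positive participant in its numerator, so false positives offset missed cases and the ratio can exceed 1

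*Combined protocol and SAP*

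**What the plan says.** Section 5, Primary Analysis, gives the estimator in one sentence: "The diagnostic sensitivity of AL will be estimated as the number of participants with REI" of at least 5 "events per hour according to AL per AASM 2012 Guidelines divided by the number of participants with AHI" of at least 5 by PSG. The result is compared with 0.825 by an exact binomial test at 0.025, with a Wilson score interval. The analysis population is everyone eligible who has at least 4 evaluable hours, whatever their PSG result.

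Other places bear on the meaning:

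- Section 3 names PSG as the comparator "which will be considered the gold standard for the estimate of sensitivity".
- Section 4.8 says the tested parameter "is the sensitivity of AL in diagnosing SDB (using a cut-off of 5 events per hour", with AHI from PSG and REI from the device.
- Section 4.8 supports the assumed sensitivity of 0.95 by noting that "13 out of 13 true positives were correctly classified in a previous study", and states that "a minimum of 56 SDB participants are required".
- Section 4.8 also sets a recruitment goal: "At least 5 participants in each of the following SDB categories (per PSG"). One of those categories is AHI below 5.
- Section 5, Secondary Analyses, reuses the estimate: "The positive likelihood ratio (the estimated sensitivity divided by 1 minus the estimated specificity").

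**The concern.** Sensitivity is the share of PSG-positive participants whom the device also calls positive. The written numerator omits the second condition and counts every device-positive participant, including any who are PSG-negative. The plan sets out to recruit such participants, so false positives are possible.

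Three things follow if the sentence is applied as it stands. A false positive raises the estimate exactly as much as a detected case does, so over-calling hides missed cases. The count is no longer a binomial number of successes among the PSG-positive participants, so the exact test does not have its stated error rate. And the count can exceed the denominator, in which case the prespecified test and interval do not exist. The positive likelihood ratio takes in the same faulty estimate.

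**Working it through.** **Inputs from the documents.** Null value 0.825; one-sided level 0.025; exact binomial test; assumed sensitivity 0.95; target power 80%; 56 SDB participants; 75 enrolled; at least 5 with AHI below 5 (Sections 4.8 and 5).

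**Assumed inputs.** The SDB/non-SDB split and the device's false-positive rate among PSG-negative participants are not given. I take all 75 as evaluable, with splits 56/19 (the largest non-SDB share that still meets the target of 56), 60/15, 65/10 and 70/5 (the recruitment floor for AHI below 5), and false-positive rates of 10%, 20% and 30%.

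**Step 1: reproduce the plan's figure.** For each n, find the smallest c with P(Bin(n, 0.825) ≥ c) ≤ 0.025, then compute P(Bin(n, 0.95) ≥ c). The first n with power of at least 0.80 is 56, with c = 52, exact level 0.0229 and power 0.853. The stated 56 is therefore the sample size for a binomial proportion among PSG-positive participants, which is ordinary sensitivity.

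**Step 2: write out both estimators.** Ordinary sensitivity is TP/(TP+FN). The Section 5 sentence gives (TP+FP)/(TP+FN). They agree only when FP = 0.

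**Step 3: type I error of the written formula.** With n₁ SDB participants and false-positive rate f, the rejection probability at true sensitivity 0.825 is P(X + Y ≥ c), where X ~ Bin(n₁, 0.825) and Y ~ Bin(75 − n₁, f). Outcomes with a ratio above 1 are counted here as rejections.

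| Split | c | Correct formula | f = 10% | f = 20% | f = 30% |
|---|---|---|---|---|---|
| 56/19 | 52 | 0.023 | 0.137 | 0.330 | 0.552 |
| 60/15 | 56 | 0.014 | 0.073 | 0.184 | 0.336 |
| 65/10 | 60 | 0.020 | 0.058 | 0.118 | 0.199 |
| 70/5 | 65 | 0.011 | 0.021 | 0.035 | 0.052 |

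If outcomes above 1 are treated instead as not rejecting, the 56/19 entries at 20% and 30% fall to 0.308 and 0.46, and the 60/15 entry at 30% falls to 0.311. The inflation remains.

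**Step 4: probability that the ratio exceeds 1 at the plan's own sensitivity of 0.95.** This is P(Bin(n₁, 0.95) + Bin(75 − n₁, f) > n₁).

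| Split | f = 10% | f = 20% | f = 30% |
|---|---|---|---|
| 56/19 | 0.249 | 0.587 | 0.826 |
| 60/15 | 0.159 | 0.418 | 0.664 |
| 65/10 | 0.073 | 0.208 | 0.379 |
| 70/5 | 0.021 | 0.057 | 0.108 |

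In these cases the exact test has more successes than trials. The Wilson square-root term, p(1−p)/n + z²/(4n²) with z = 1.96, is already negative at one count above n for n = 56, 60, 65 and 70.

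**Step 5: a single data set.** Take 60 SDB participants, 53 of them detected, and 3 false positives among 15 others. Correctly, 53/60 = 0.883 with p = 0.153, so the null is not rejected. As written, (53+3)/60 = 56/60 = 0.933 with p = 0.014, so it is.

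**Step 6: the likelihood ratio.** With 58/60 detected and 3/15 false positives, the correct value is (58/60)/(3/15) = 4.83. With the written sensitivity it is (61/60)/(3/15) = 5.08. The point estimate moves across 5, but the lower 97.5% limits on the log scale are about 1.75 and 1.85, so the formal comparison with 5 would not change in this example.

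**The case against.** The best defence is that nobody would compute it this way. The word sensitivity is used throughout, PSG is named the gold standard, Section 4.8 sizes on SDB participants, and the exact binomial test and Wilson interval make sense only if the successes are a subset of the trials. Section 4.11.8 has an independent statistician do the analysis, and that person would probably use TP/(TP+FN). Section 4.8 also writes no rival numerator; the conflict is with its parameter, its sizing and its rationale. All of this stands, and it makes a drafting slip the likely explanation.

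It is also fair that the size of the problem rests on assumed inputs. At 70/5 with a 10% false-positive rate the written formula gives 0.021, inside the nominal level, and the largest figures need many PSG-negative participants and a high false-positive rate. The secondary likelihood ratio partly guards against over-calling: at sensitivity 0.825 a ratio of 5 needs a false-positive rate of at most 0.825/5 = 16.5%.

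None of this removes the defect. No other section supplies the missing condition, so an analyst who computes sensitivity correctly departs from the only written formula, and does so in the direction that can only lower the estimate or leave it unchanged. That choice should be settled before data are seen. The likelihood ratio is secondary, does not gate the primary claim, and uses the same estimate.

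**Conclusion.** The concern holds: the primary formula is wrong as written. Its result is incorrect whenever there is at least one false positive. The error-rate figures apply only if the sentence is executed literally, and they depend on the assumed split and false-positive rate. The effect is small near the floor of 5 non-SDB participants and large near 19. That the ratio is not sensitivity, and that it can exceed 1, needs no assumption beyond the possibility of false positives. Because this is the sole primary endpoint and the sentence is its only working definition, it must be corrected.

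**What to change.** Replace the estimator sentence in Section 5. Define sensitivity as the number of participants with both REI of at least 5 on the device and AHI of at least 5 on PSG, divided by the number with AHI of at least 5 on PSG, with both tests scored per AASM 2012. State that this numerator and denominator feed the exact binomial test, the Wilson interval and the positive likelihood ratio. Define the 2007 likelihood ratio in the same way under 2007 scoring.

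The cost is one sentence and a cross-reference. No new data are needed, and the requirement of 56 SDB participants (52 of 56 to succeed, level 0.0229, power 0.853 at 0.95) is unchanged. The only downside for the sponsor is that the estimate can stay the same or fall.

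### Does the Wilson interval reported beside the exact binomial test leave the primary conclusion open to contradiction?

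*Combined protocol and SAP*

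**What the plan says.** Section 4.8 sets the null hypothesis that sensitivity is 0.825 or lower and names the test: "The hypothesis will be tested with an exact binomial test using a one-sided significance level of 0.025". Section 5, under the primary analysis, repeats this: "The diagnostic sensitivity of AL will be compared to the threshold of 0.825", and this is to be done "with an exact binomial test, using a significance level of 0.025". The next sentence adds an interval: "Further a one-sided 97.5% confidence interval for the diagnostic sensitivity will be calculated using the Wilson score method".

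On numbers, Section 4.8 assumes a true sensitivity of 0.95 and states: "To achieve an 80% probability of rejecting the null hypothesis, a minimum of 56 SDB participants are required". It also says: "Seventy-five participants will be enrolled in order to meet recruitment goals". One of those goals is at least 5 participants with no SDB on polysomnography (PSG).

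**The concern.** The test and the interval share one threshold (0.825), one direction and one error level (0.025 and 97.5%). A reader will naturally expect a lower bound above 0.825 to mean that the test rejects. That equivalence holds for the Clopper-Pearson bound, which inverts the exact binomial test. It does not hold for the Wilson bound, which inverts the score test.

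The number of SDB participants is known only after the PSGs are scored, so a discordant denominator cannot be ruled out in advance. The primary objective is worded as showing a sensitivity of at least 0.825. At a discordant result, the report would print a 97.5% lower bound just above 0.825 beside a failed primary test. If the plan left open which of the two decides, someone could later lean on the more favourable one.

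**Working it through.** **Inputs.** Threshold p0 = 0.825, one-sided level 0.025, assumed true sensitivity 0.95, minimum of 56 SDB participants, 75 enrolled, at least 5 without SDB (Sections 4.8 and 5). The Wilson bound is taken without continuity correction (z = 1.96), and the numerator as true positives among PSG-positive participants.

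**The plan's own figure.** For each n, find the smallest r with P(X ≥ r | n, 0.825) ≤ 0.025; power is P(X ≥ r | n, 0.95). At n = 55, r = 52 and power is 0.705. At n = 56, r = 52, the exact level is 0.0229 and power is 0.853. The first n with at least 80% power is 56, as stated.

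**Where test and interval part.** With p = x/n, the Wilson lower bound is

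L = [p + z²/(2n) − z√(p(1−p)/n + z²/(4n²))] / (1 + z²/n).

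For 58/63: (0.9206 + 0.0305 − 1.96 × 0.03744) / 1.0610 = 0.8273, while P(X ≥ 58 | 63, 0.825) = 0.0257. The bound clears 0.825 and the test fails. Over n = 40 to 75 the discordant results are:

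| Result | Exact p | Wilson bound | Clopper-Pearson bound | Test needs |
|---|---|---|---|---|
| 44/47 | 0.0254 | 0.8284 | 0.8246 | 45 |
| 51/55 | 0.0259 | 0.8274 | 0.8241 | 52 |
| 58/63 | 0.0257 | 0.8273 | 0.8244 | 59 |
| 64/70 | 0.0279 | 0.8253 | 0.8227 | 65 |

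With 75 evaluable participants and both targets met, n runs from 56 to 75 − 5 = 70. The methods agree at 13 of these 15 values and differ by one count at 63 and at 70. At the planned minimum of 56, both need 52. They also agree at 71 to 75, should the goal for participants without SDB be missed.

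**How often.** Given n = 63, the chance of exactly 58 is 11.2% at true sensitivity 0.95; given n = 70, the chance of exactly 64 is 7.7%. These must be weighted by the chance of meeting that n. The documents give no SDB share, so a range of 65% to 85% of 75 is assumed. The overall chance is the sum over discordant n of Binomial(n; 75, share) × Binomial(x; n, 0.95):

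| SDB share | All four results | Only n ≥ 56 |
|---|---|---|
| 65% | 2.33% | 0.002% |
| 70% | 2.15% | 0.03% |
| 75% | 1.89% | 0.24% |
| 80% | 1.57% | 0.95% |
| 85% | 1.53% | 1.47% |

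At true sensitivity 0.925, the largest value with n ≥ 56 is 2.44%. At the lower shares nearly all of the middle column comes from n = 47 and 55, below the plan's own minimum. There the shortfall of SDB participants would matter far more than the interval method.

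**Which result decides.** Section 4.8 names one test for the hypothesis. Section 5 compares sensitivity with 0.825 by that same test. The interval sentence mentions no threshold and no comparison. One method is tied to 0.825, in two places; the other is an added estimate.

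**Is Wilson a poor interval here?** One-sided coverage at a true sensitivity of 0.825 is 1 − P(X ≥ r | n, 0.825), with r the smallest count whose bound exceeds 0.825. For Clopper-Pearson, the miss probabilities over n = 56 to 70 sum to 0.2357; 0.2357/15 = 0.0157, so average coverage is 98.4%. Wilson differs only at n = 63 (0.0257 instead of 0.0092) and n = 70 (0.0279 instead of 0.0109). Its sum is 0.2357 + 0.0165 + 0.0170 = 0.2692; 0.2692/15 = 0.0179, so average coverage is 98.2%. Its minimum is 1 − 0.0279 = 97.2%, at n = 70. On average it is still conservative, and its worst value is 0.3 percentage points below nominal.

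**Effect of a swap.** At 52/56 the bound would move from 0.830 to 0.827, and both pass. No critical count of the test changes.

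**The case for a change.** The best case for a change is that it costs almost nothing. Clopper-Pearson matches the exact test at every n from 40 to 75, so one phrase in Section 5 would make contradiction impossible. Wherever the two disagree, Wilson favours the device, and such matters are best settled before data are seen. The sponsor writes the study report, and no sentence says how to read a disagreement.

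The arithmetic behind this stands, and so does the remark that a report at 58/63 or 64/70 would need a line of explanation. The step from there to an ambiguity in the plan does not. A sentence saying that the exact test governs would repeat what Sections 4.8 and 5 already establish. An interval given for estimation need not invert the test: many statisticians choose Wilson because its coverage lies closer to nominal than the more conservative Clopper-Pearson interval, and others prefer strict duality. Both are defensible.

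**Conclusion.** The concern does not hold. The mismatch is real but confined to a single result at each of two denominators in the planned range, 63 and 70, where Wilson clears 0.825 by 0.0023 and 0.0003. The exact test is the only decision rule in the plan, so the primary conclusion, its error rate, the power and the sample size are unaffected. A bound about 0.003 lower would gain nothing of substance.

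This rests on three assumptions. First, Wilson is used without continuity correction, the usual reading of the name. A corrected version would not be discordant at 55, 63 or 70; it would be stricter than the test at 56–58, 64–66 and 71–73, and would still decide nothing. Second, the numerator counts true positives among PSG-positive participants, although Section 5 words the ratio more loosely. Third, the overall probabilities depend on the assumed SDB share of 65% to 85%. The conclusion that the exact test decides depends on none of these.
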